### 5.2 Secondary Endpoints

### 5.2.1 Proportions of success in average pain intensity during Weeks 1-4 of home trial

The proportion of subjects who successfully achieve  $\geq 50\%$  reduction from baseline in Group #1 during Weeks 1-4 of the 8-week home trial will be compared to that in Group #2 during Weeks 1-4 of the sham period using a Fisher's exact test. The pain intensity scores will be determined for each subject by applying the same method used for the primary endpoint: taking the mean of the daily average pain intensity (BPI-SF Question #5) reported in the 7-day diary at baseline compared to the mean score for the same regions of pain reported over Weeks 1-4 of treatment (*i.e.*, the average of all scores in the diaries during this period) for Group #1 and Group #2. To be considered a success, subjects must have  $\geq 50\%$  reduction in pain. The null hypothesis is that there is no difference in the proportions of success between the two treatment groups, versus the alternative hypothesis, that the proportions of success differ from one another. Testing will be conducted at the 0.05 level of significance.

### 5.2.2 Long-term Durability of Pain Relief at 3, 6, 9, and 12 months after SOT

The analysis of the durability of the treatment effect on average pain intensity will be conducted at 3, 6, 9, and 12 months after the start of therapy by comparing the proportion of subjects who successfully achieve  $\geq 50\%$  reduction from baseline in Group #1 at each time point compared to 3 months after the start of therapy (the longest follow-up before crossover) in Group #2 using a Fisher's exact test. The pain intensity scores will be determined for each subject by applying the same method used for the primary endpoint: taking the mean of the daily average pain intensity (BPI-SF Question #5) reported in the 7-day diary at baseline compared to the mean score reported in the follow-up diary (*i.e.*, 3, 6, 9, or 12 months after SOT for Group #1; compared to 3 months after SOT in Group #2). To be considered a success, subjects must have  $\geq 50\%$  reduction in pain. The null hypothesis is that there is no difference in the proportions of success between the two treatment groups, versus the alternative hypothesis, that the proportions of success differ from one another. Testing will be conducted at the 0.05 level of significance.

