# 2.2 Percutaneous PNS has been tested to treat pain in patients following orthopedic surgery in prior studies.

Ten subjects that had undergone TKR and were experiencing postoperative pain were enrolled. Of these subjects, 6 subjects were tested between postoperative day (POD) 6-14, and 4 subjects were tested between POD 40-100. The femoral and/or sciatic nerves were targeted using leads placed percutaneously, and the target nerve(s) were selected based on the location of pain (e.g., front or back of the knee). Leads targeting the femoral nerve were placed by inserting the introducer needle distal to the femoral crease and lateral to the femoral nerve, while leads targeting the sciatic nerve were placed using a trans-gluteal or popliteal approach. Stimulation amplitude and pulse duration were adjusted to provide comfortable sensations covering the regions of pain. Subjects rated their "Pain Right Now" on the Brief Pain Inventory Short Form (Question 6, BPI-6) with stimulation off and stimulation on. In 9 subjects (90%), pain at rest was reduced by a highly clinically significant amount (≥50%) with stimulation on (mean=1.4) compared to stimulation off (mean=5.4), with an average reduction of 75%. All leads were removed without discomfort or complication in a brief, out-patient procedure (i.e., subjects did not take stimulation system home).

In another prospective case series study, subjects underwent lead placement 0-14 days prior to total knee replacement and received PNS following surgery for up to 6 weeks. Postoperatively at 1 month following surgery, the average pain over the previous week was mild and well-controlled ( $\leq$ 4/10) in 15/18 subjects (83%). Fourteen of 18 subjects (77%) had ceased opioid use by 62 days following surgery (*i.e.*,  $\leq$ 25% of subjects still using opioids). At 3 months following surgery, 17 subjects (94%) had pain of  $\leq$  2/10, and 16 subjects (89%) had ceased opioid use. Overall, these results compared favorably to historical controls: persistent pain of  $\geq$ 3 months after TKR is typically reported in 10-20% or more of patients[3, 8, 20, 24, 76, 77], and

25-40% of patients continue to use opioids at 90 days (3 months) after TKR[ $\underline{34}$ ,  $\underline{78}$ ,  $\underline{79}$ ].

3.0 Device Description This study utilizes the commercially available SPRINT® PNS System. Electrical stimulation will be applied via leads in the affected limb

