### 4.4.2 Secondary Endpoints

Secondary endpoints will be collected to evaluate what effect, if any, the interventions have on each measure. Changes from baseline will be evaluated as secondary efficacy endpoints for the following outcome measures:

- Durability of the treatment effect on average pain intensity
- Average pain over the past week (BPI-5)
- o Pain medication usage
- Pain Catastrophizing Scale (PCS)
- Patient Global Impression of Change (PGIC)
- o Pain Interference (BPI-9)
- Western Ontario McMaster Universities Osteoarthritis Index (WOMAC)
- 6 minute walk test (6MWT)

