### 4.2 Secondary Hypotheses

The Secondary null  $(H_0)$  and alternative hypotheses  $(H_a)$  are:

1) Proportions of success in average pain intensity between groups for Weeks 1-4. The null (H0) and alternative hypotheses (Ha) are:

H0: 
$$p_{G1} - p_{G2} = 0$$
 vs.

Ha: 
$$p_{G1} - p_{G2} \neq 0$$

where p G1 and p G2 are the proportions of success for average pain intensity during Weeks 1-4 in Group #1 and during Weeks 1-4 in Group #2, respectively.

2) Proportions of success in average pain intensity (durability of primary endpoint) at 3, 6, 9, and 12 months after SOT

H0: 
$$p_{G1} - p_{G2} = 0$$
 vs.

$$H_a: p_{G1} - p_{G2} \neq 0$$

where p G1 and p G2 are the proportions of success for average pain intensity at follow up (3, 6, 9, and 12 months after SOT in Group #1 and 3 months after SOT in Group #2).

3) Mean average pain relief at specified intervals after start of therapy

H0: 
$$u_{G1} - u_{G2} = 0$$
 vs.

$$H_a$$
:  $u_{G1} - u_{G2} \neq 0$ 

where u G1 and u G2 are the mean percent improvement in average pain intensity at specified intervals after start of therapy (Weeks 1-4, Weeks 5-8, and 3, 6, 9, and 12

months after SOT in Group #1 and Weeks 1-4, Weeks 5-8, and 3 months after SOT in Group #2).

4) Pain medication usage at specified intervals after start of therapy (opioid, non-opioid and total analgesic medication usage analyzed separately)

H0: 
$$p_{G1} - p_{G2} = 0$$
 vs.

Ha: 
$$p_{G1} - p_{G2} \neq 0$$

where p G1 and p G2 are the distribution probabilities for pain medication usage at monthly intervals (Weeks 1-4, Weeks 5-8, and 3, 6, 9, and 12 months after SOT in Group #1 and Weeks 1-4, Weeks 5-8, and 3 months after SOT in Group #2).

5) Pain Catastrophizing Scale (PCS) at specified intervals after start of therapy

$$H_0$$
:  $u_{G1} - u_{G2} = 0$  vs.

$$H_a$$
:  $u_{G1} - u_{G2} \neq 0$ 

where u G1 and u G2 are the mean percent improvement in PCS at specified intervals after start of therapy (4 weeks, 8 weeks after SOT in Group #1 and 4 weeks, 8 weeks after SOT in Group #2).

6) Patient global impression of change (PGIC) at specified intervals after start of therapy

H0: 
$$u_{G1} - u_{G2} = 0$$
 vs.

Ha: 
$$u_{G1} - u_{G2} \neq 0$$

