### 5.0 Endpoint Analyses

Analyses of the primary and secondary effectiveness endpoints will be conducted on the full analysis set and the per-protocol population set at each specified study interval. The full analysis

set is considered the primary population for formal statistical hypothesis testing.
5.1 Primary Endpoint  Relief of postoperative pain will be evaluated using the average pain intensity. All subject will record pain scores daily for the qualifying knee (i.e., with total knee implant and qualifyin pain) in the 7-day diaries using BPI-SF Question #5. Data will be collected  Each subject must have ≥50% reduction is
pain relative to baseline to be considered a success in the primary efficacy endpoint analysis. Missing data will be handled according to Section 8.2. The primare endpoint analysis will be based upon the Full Analysis Set, including imputation for missing data due to missed visits and early termination. An analysis will also be performed based on the Perotocol population,
Group #1 will receive active stimulation and Group #2 wi receive sham stimulation during the 8-week home trial.
The primary endpoint compares the proportion of subjects in Group #1 relative to that in Group #2 that achieve $\geq 50\%$ reduction in pain from baseline to Weeks 5-8 of the home trial using Fisher's exact test. The null hypothesis (H 0 ) is that the PNS treatment (Group #1, activational stimulation) is equal to the control (Group #2, sham stimulation) in providing pain relief. The alternative hypothesis (H a ) is that Group #1 has a proportion of successes that is not equal to the

 $H_0$ : proportion of successes in Group #1 = proportion of successes in Group #2  $H_a$ : proportion of successes in Group #2  $\neq$  proportion of successes in Group #2

If the proportion of successes in the PNS treatment is larger than the proportion of successes in the control during the Weeks 5-8 of the home trial and statistically significantly different (p < 0.05, two-sided), then the null hypothesis is rejected at the 0.05 level of significance, which will indicate that the therapeutic effect is clinically significant and superior to the placebo effect[2].

proportion of successes in Group #2.

treatment effect for time from TKR.

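### SAP 5.2.2 reports success at each later visit as durability: it cannot tell retained responders from late gains, and at 6 to 12 months it has no concurrent control

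*SAP*

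**What the plan says.** Protocol 4.4.2 lists as a secondary endpoint "Durability of the treatment effect on average pain intensity". SAP 4.2, item 2, names the matching hypothesis: "Proportions of success in average pain intensity (durability of primary endpoint) at 3, 6, 9, and 12 months after SOT". The primary endpoint to which that label points is success in Weeks 5-8 (Protocol 4.4.1.1; SAP 4.1 and 5.1).

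SAP 5.2.2 sets out the analysis: "The analysis of the durability of the treatment effect on average pain intensity will be conducted at 3, 6, 9, and 12 months". It and the sections around it fix four things:

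- **Score.** Success is a reduction of at least 50%, taken from the mean daily pain "reported in the 7-day diary at baseline compared to the mean score reported in the follow-up diary". Only these two diaries enter.
- **Comparator and test.** Group #1 at each time point is "compared to 3 months after the start of therapy (the longest follow-up before crossover) in Group #2 using a Fisher's exact test". SAP 4.2 gives the same layout: "3, 6, 9, and 12 months after SOT in Group #1 and 3 months after SOT in Group #2".
- **Population.** SAP 5.0 sets it for all effectiveness endpoints: "Analyses of the primary and secondary effectiveness endpoints will be conducted on the full analysis set and the per-protocol population set at each specified" interval. SAP 6.2 asks for available Weeks 5-8 data, not for a response in those weeks.
- **Status.** SAP 4.0 makes all secondary hypotheses exploratory, tested at 0.05 two-sided without adjustment and without claims of significance.

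**The concern.** Durability of a Weeks 5-8 success suggests that the success was followed forward to see whether it lasted. The planned score does not do that. A subject who failed on treatment and improved months after lead removal counts as a durability success. A responder who relapsed can be offset by such a subject, and the reported percentage does not move. No visible analysis shows how many Weeks 5-8 successes were kept. SAP 5.2.3 (mean percent improvement) is also computed visit by visit, so it does not fill the gap.

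A second feature adds to this from 6 months on. Group #2 contributes only its 3-month result, while Group #1 has had 3, 6 or 9 further months in which pain can change for reasons unrelated to stimulation. A reader of a 12-month durability percentage would probably take it as relief that began on treatment and lasted. The planned figure cannot show that.

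**Working it through.** The sample size and its assumptions are not shown in the public text, so there is no planned figure to reproduce. Every rate and arm size below is an assumption.

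**Step 1: what the later percentage contains.** Let *s* be the share succeeding in Weeks 5-8, *k* the fraction of those still successes later, and *g* the fraction of the others who succeed later.

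- Planned figure = s·k + (1 − s)·g
- Sustained success = s·k

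With s = 0.40, k = 0.50, g = 0.25:

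- Planned: 0.40 × 0.50 + 0.60 × 0.25 = 0.20 + 0.15 = 0.35
- Sustained: 0.20
- Set against the 40% in Weeks 5-8, the planned figure looks like 0.35/0.40 = 87.5% retained. True retention is 50%.

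**Step 2: range, with s = 0.40.** Take relapse of 30-60% (k from 0.70 to 0.40) and late recovery of 15-35%.

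- Lowest: (0.40 × 0.40 + 0.60 × 0.15)/0.40 = 0.25/0.40 = 62.5% apparent, 40% true
- Highest: (0.40 × 0.70 + 0.60 × 0.35)/0.40 = 0.49/0.40 = 122.5% apparent, 70% true

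A separate grid with s of 0.3 or 0.5, k of 0.6 or 0.9 and g from 0.1 to 0.4 gives the share of counted successes that are late gains. It runs from 0.05/0.50 = 10% (s = 0.5, k = 0.9, g = 0.1) to 0.28/0.46 = 61% (s = 0.3, k = 0.6, g = 0.4).

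**Step 3: the contrast between arms, with no treatment effect at all.** Group #2 has 3-month success p3. Group #1 at a later visit has p3 + (1 − p3)·g, where g is now the recovery among 3-month non-responders and no 3-month success relapses. For example, p3 = 0.20 and g = 0.20 give 0.20 + 0.80 × 0.20 = 0.36, a gap of 16 points. The two-sided Fisher test at 0.05 was enumerated exactly for p3 of 0.20 and 0.30 and for 25, 50 and 75 per arm.

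| Setting | Gap | Test significant in favour of Group #1 |
|---|---|---|
| 3 months, concurrent (g = 0) | 0 points | 1.1-1.6% (2.2-3.3% in either direction) |
| Later visit, g = 0.10 | 7-8 points | 4-16% |
| Later visit, g = 0.20 | 14-16 points | 12-52% |
| Later visit, g = 0.30 | 21-24 points | 26-86% |

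The 3-month test keeps its level. The later tests do not if Group #1 improves with time. Relapse among 3-month successes would shrink these gaps, and a net worsening would turn the error against Group #1.

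**The case against.** Much of the opposing case stands.

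- **The 3-month result is sound.** A reader might infer that natural recovery inflates it too. It does not. Both arms are randomised, observed at the same time, and blinded through Visit 11 (Protocol 5.2.1; SAP 3.1), so natural recovery cancels in the difference. The protocol speaks of a treatment effect, and the proportion of all subjects against a concurrent control is a valid treatment-policy measure of one.
- **The later bias comes from the fixed comparator.** With a concurrent control at 6, 9 and 12 months, the same all-subject proportion would be acceptable. Ignoring Weeks 5-8 status does not by itself bias the contrast.
- **The protocol's background does not show that late recovery is to be expected here.** Protocol 2.2 says that persistent pain of at least 3 "months after TKR is typically reported in 10-20% or more of patients", which might suggest that most subjects will improve. But that describes knee replacement patients in general, timed from surgery. This trial selects people whose pain has persisted (Protocol 4.2.1.2), and Protocol 2.1 says that uncontrolled pain can become chronic and last for years.
- **Most responders relapsing behind a flat percentage is a corner case.** At s = 0.40 with half lost, a flat figure needs late recovery of 0.20/0.60 = 33%. With 60% lost it needs 0.24/0.60 = 40%, outside the range used above.
- **Replacing the tested endpoint with success at both times is a preference, not a correction.** It would exclude delayed responders and partly restate the primary result. It would also count noise around the 50% threshold as loss, since later visits use a 7-day diary and Weeks 5-8 average all diary scores in that period.
- **Exploratory status and redaction.** No significance claims will be made. The content of SAP 5.2.10, 8.0 and 8.2 is not shown and may already include a sustained-response analysis.

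What remains is that the visible plan never links later success to Weeks 5-8 success, although its label says that it does, and that its tests at 6 to 12 months have no concurrent control.

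**Conclusion.** The point holds in a limited form. At all four time points the figure is success at that visit, not persistence of the Weeks 5-8 success. That is a gap in labelling and reporting. At 3 months the comparison between arms is valid as planned. At 6, 9 and 12 months, change over time in Group #1 alone enters the comparison and, if it is improvement, can be read as durable effect.

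The size cannot be taken from the documents, which give no recovery or relapse rate for this population. The 35% against 20%, and the rejection rates under no effect, show only what can happen under the stated assumptions. Severity is limited because the secondary tests are exploratory. The change is still worth making, since diaries already planned can answer the durability question.

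**What to change.** In SAP 5.2.2, with matching wording in SAP 4.2, item 2:

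1. Keep the all-subject proportion with at least 50% relief, and label it 'success at visit'.
2. Test between arms at 3 months only. Report the 6-, 9- and 12-month results for Group #1 descriptively.
3. Add a descriptive table for the Full Analysis Set that crosses Weeks 5-8 success with later-visit success: sustained, lost, late gain, neither. Show both arms at 3 months and Group #1 thereafter, with the share of Weeks 5-8 successes retained.
4. If a redacted section already contains this analysis, refer to it from 5.2.2.

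The cost is SAP wording and one more table, with no new data, visits or subjects. Sustained percentages will be lower than the visit percentages, some apparent loss will be noise around the 50% threshold, and the exploratory p-values at 6 to 12 months are given up.

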where u G1 and u G2 are the mean scores for PGIC at specified intervals after start of therapy (4 weeks, 8 weeks, and 3, 6, and 12 months after SOT in Group #1 and 4 weeks, 8 weeks, and 3 months after SOT in Group #2).

7) Pain Interference (BPI-9) at specified intervals after start of therapy

H0: 
$$p_{G1} - p_{G2} = 0$$
 vs.

Ha: 
$$p_{G1} - p_{G2} \neq 0$$

where p G1 and p G2 are the proportions of success for pain interference at specified intervals after start of therapy (4 weeks, 8 weeks, and 3, 6, 9, and 12 months after SOT in Group #1 and 4 weeks, 8 weeks, and 3 months after SOT in Group #2).

8) Physical recovery (Western Ontario and McMaster Universities Osteoarthritis Index; WOMAC) at specified intervals after start of therapy

$$H_0$$
:  $p_{G1} - p_{G2} = 0$  vs.

$$H_a$$
:  $p_{G1} - p_{G2} \neq 0$ 

where p G1 and p G2 are the proportions of success for WOMAC at specified intervals after start of therapy (8 weeks, and 3, 6, and 12 months after SOT in Group #1 and 8 weeks and 3 months after SOT in Group #2).

9) 6MWT at specified intervals after start of therapy

H0: 
$$u_{G1} - u_{G2} = 0$$
 vs.

Ha: 
$$u_{G1} - u_{G2} \neq 0$$

where u G1 and u G2 are the mean percent improvement on the 6MWT at specified intervals after start of therapy (8 weeks and 3 months after SOT).

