### 5.2.3 Mean pain relief for Weeks 1-4, Weeks 5-8, and 3, 6, 9, and 12 months after SOT

The analysis of treatment effect on average pain compares the mean percent improvement from baseline to the specified intervals after start of therapy. The mean percent improvement in Group #1 for Weeks 1-4, Weeks 5-8, and 3 months will be compared to Group #2 for Weeks 1-4, Weeks 5-8, and 3 months, respectively. The mean percent improvement in Group #1 at 6, 9, and 12 months will be compared to Group #2 at 3 months (the longest follow-up before crossover). A two-sided Wilcoxon rank-sum test will be performed to assess the difference between groups.

During the home trial (*i.e.*, Weeks 1-4 or Weeks 5-8 of the home trial), the average pain intensity scores will be determined for each subject by taking the mean of the daily average (BPI-SF Question #5) reported in the 7-day diary at baseline compared to the mean score for in the 7-day diaries during Weeks 1-4 or Weeks 5-8 of the home trial, respectively

Similarly, at 3, 6, 9, or 12 months after start of therapy, the mean
verage pain intensity scores will be determined by taking the mean of the daily average pain (BPI-
F Question #5) reported in the 7-day diary at baseline compared to the mean pain score in the 7-
ay diaries preceding each visit
. The null hypothesis is that the distribution of mean change in
verage scores is the same for the two groups; the alternative hypothesis is that one of the
istributions is shifted relative to the other distribution by a constant amount. Testing will be
onducted at the 0.05 level of significance.

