# 5.2.4 Pain Medication Usage at 4 weeks, 8 weeks, and 3, 6, 9, and 12 months after SOT 1) Pain medication usage between groups

The analysis of pain medication usage examines changes in medication usage between the two groups. Changes in medication will be reviewed for Weeks 1-4 of therapy, Weeks 5-8 of therapy, and at 3, 6, and 12 months after the start of therapy. For this analysis, a blinded third-party medication committee will review medications of study participants collected for each diary collection period and will use the following convention for scoring medication changes, in comparison to the baseline diary medications:

- No change = No change in dosage or change is not clinically meaningful to impact pain outcomes.
- Increase = Clinically meaningful increase in medication that would impact pain outcomes.
- **Decrease** = Clinically meaningful decrease in medication that would impact pain outcomes.

The blinded third-party medication committee (comprised of three clinicians experienced in the treatment and management of pain) will serve as the evaluator for all clinical sites. Final determinations of changes in medication usage will require agreement among at least two of the three blinded evaluators. In cases where there is 1:1:1 tie, the medication review committee will convene to discuss and adjudicate the final determination.

The distribution of changes in opioid pain medication usage (decrease/no change/increase) will be reported first using an exact Mantel-Haenszel test to compare the ordered distributional responses (percentage of subjects within each category) between Group #1 and Group #2. Group #1 at Weeks 1-4, Weeks 5-8, and 3 months will be compared to Group #2 at Weeks 1-4, Weeks 5-8, and 3 months, respectively. Group #1 at 6, 9, and 12 months will be compared to Group #2 at 3 months (the longest follow-up before crossover). Assuming there is a statistically significant difference in the ordered distributional responses between Group #1 and Group #2 at a given timepoint, a subsequent statistical test will be carried out to compare between groups the percent of subjects categorized as having a decrease in opioid pain medication. In addition to opioids, this analysis will also be repeated for analysis of all pain medications, and non-opioid analgesic usage independently.

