# 5.2.6 Patient Global Impression of Change at 4 weeks, 8 weeks, and 3, 6, 9, and 12 months after SOT

The analysis of treatment effect on the PGIC compares the rank scores (of 7 possible ranks, ranging from -3 to 0 to +3, where -3 is very much worse, 0 is no change, and +3 is very much improved) of Group #1 to Group #2. The mean rank score of Group #1 at 4 weeks, 8 weeks, and 3 months will be compared to Group #2 at 4 weeks, 8 weeks, and 3 months, respectively. The mean rank score of Group #1 at 3, 6, and 12 months will be compared to Group #2 at 3 months (the longest follow-up before crossover). The difference between groups will be evaluated with a Wilcoxon rank-sum test. The null hypothesis is that there is no difference in the mean rank score between the two treatment groups, versus the alternative hypothesis, that the mean rank scores differ from one another. Testing will be conducted at the 0.05 level of significance.

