### 5.2.7 Pain Interference at 8 weeks, and 3, 6, 9, and 12 months after SOT

The analysis of the treatment effect on pain interference compares the proportion of subjects who successfully achieve  $\geq 50\%$  reduction in average pain interference score in Group #1 at each time point relative to that in Group #2 based on a Fisher's exact test. Relief of pain interference will be evaluated using the average pain interference (BPI-SF Question #9). The baseline average pain interference score will be compared to the average pain interference score at each specified interval after start of therapy to determine the percent reduction in pain interference. To be considered a success, subjects must have  $\geq 50\%$  reduction in the average pain interference score. The proportion of success in Group #1 at 4 weeks, 8 weeks, and 3 months will be compared to Group #2 at 4 weeks, 8 weeks, and 3 months, respectively. The proportion of success in Group #1 at 3, 6, and 12 months will be compared to Group #2 at 3 months (the longest follow-up before crossover). The null hypothesis is that there is no difference in proportions of success between the two treatment groups, versus the alternative hypothesis, that the proportions of success differ from one another. Testing will be conducted at the 0.05 level of significance.

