# 5.2.8 Western Ontario and McMaster Universities Osteoarthritis Index (WOMAC) at 8 weeks, 3, 6, 9, and 12 months after SOT

[figure not shown]
The analysis of treatment effect on function (*i.e.*, physical recovery) compares the proportion of subjects who successfully achieve  $\geq$  33% improvement[3-5] in average WOMAC score in Group #1 at each time point relative to that in Group #2 based on a Fisher's exact test. The WOMAC questionnaire assesses physical recovery and includes 24 items assessing pain, stiffness, and difficulty with daily activities. Each item is scored on an 11-point numerical rating scale from 0-10 with lower numbers indicating improved physical recovery, and the total score is calculated.

[figure not shown]
The WOMAC scores will be collected at baseline and compared to the WOMAC scores at each specified interval after start of therapy to determine the percent improvement (*i.e.*, reduction in score) in physical recovery. To be considered a success, subjects must have  $\geq 33\%$  reduction in the WOMAC score. The proportion of success in Group #1 at 8 weeks and 3 months will be compared to Group #2 at 8 weeks and 3 months, respectively. The null hypothesis is that there is no difference in proportions of success between the two treatment groups, versus the alternative hypothesis, that the proportions of success differ from one another. Testing will be conducted at the 0.05 level of significance.

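### The 6, 9 and 12 month between-group tests compare Group #1 with sham at 3 months, so they cannot show durability of effect versus sham

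*SAP*

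**What the plan says.** SAP 5.2.2 presents its analysis as one of durability of the treatment effect. Using Fisher's exact test at the 0.05 level, it compares the proportion of responders "in Group #1 at each time point compared to 3 months after the start of therapy (the longest follow-up before crossover) in Group #2". Hypothesis 2 in SAP 4.2 defines the two proportions the same way: "3, 6, 9, and 12 months after SOT in Group #1 and 3 months after SOT in Group #2".

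The rule recurs:

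- SAP 5.2.3, mean pain relief: "The mean percent improvement in Group #1 at 6, 9, and 12 months will be compared to Group #2 at 3 months".
- SAP 5.2.4, pain medication: "Group #1 at 6, 9, and 12 months will be compared to Group #2 at 3 months", for opioids, non-opioids and all analgesics.
- SAP 5.2.6, PGIC: "The mean rank score of Group #1 at 3, 6, and 12 months will be compared to Group #2 at 3 months".
- SAP 5.2.7, pain interference: "The proportion of success in Group #1 at 3, 6, and 12 months will be compared to Group #2 at 3 months".

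WOMAC is unclear. The SAP 5.2.8 heading lists visits to 12 months and its opening sentence tests success "in average WOMAC score in Group #1 at each time point relative to that in Group #2", but the pairs it spells out are 8 weeks and 3 months only. Hypothesis 8 gives "8 weeks, and 3, 6, and 12 months after SOT in Group #1 and 8 weeks and 3 months after SOT in Group #2".

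Other relevant provisions:

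- **Sham follow-up.** Group #2 subjects either cross over to active stimulation or are discharged (Protocol Synopsis; SAP Table 1).
- **Blinding.** Subjects are blinded to the close of Visit 11, at 3 months (SAP 3.1). Blinded evaluators administer surveys only through Visit 11 (Protocol 7.1).
- **Status of the tests.** SAP 4.0 makes all secondary hypotheses exploratory, rules out claims of significance and applies no multiplicity adjustment.
- **Analysis sets.** SAP 5.0 runs secondary analyses on both the full analysis set and the per-protocol set.

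**The concern.** A between-group comparison estimates a treatment effect when the groups differ only in treatment. At 6, 9 and 12 months they also differ in time since start of therapy, by 3, 6 and 9 months. Pain after knee replacement may improve or worsen over that time for reasons unrelated to stimulation, and any such change enters the contrast as if it were treatment effect.

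The conditions of measurement differ too. The sham value is collected under blinding. Group #1's later diaries and questionnaires are completed after the point to which blinding is stated to hold. The documents do not say when each subject learns the assignment, so this is a loss of protection, not proof of unblinding.

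At stake is whether the trial can say that benefit over sham lasts to 12 months. These tests would yield p-values that look like evidence for or against that statement and are neither.

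**Working it through.** **1. What the contrast estimates.** Let p1(t) and p2(t) be the success proportions at month t in Group #1 and in Group #2 had it stayed on sham. For 12 months:

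p1(12) − p2(3) = [p1(12) − p2(12)] + [p2(12) − p2(3)]

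The first bracket is the durability effect. The second is change over time without active treatment. No sham subject is followed beyond 3 months, so no data in the trial can estimate the second bracket or separate the two. The same holds at 6 and 9 months, and for means and distributions.

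**2. How many tests are affected.** From the comparison sentences in SAP 5.2:

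| Section | Later times | Tests |
|---|---|---|
| 5.2.2 pain success | 6, 9, 12 | 3 |
| 5.2.3 mean pain relief | 6, 9, 12 | 3 |
| 5.2.4 medication, 3 classes | 6, 9, 12 | 9 |
| 5.2.6 PGIC | 6, 12 | 2 |
| 5.2.7 interference | 6, 12 | 2 |

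3 + 3 + 9 + 2 + 2 = 19, each run on two overlapping analysis sets. The count depends on which sentence governs. The review list in 5.2.4 omits 9 months although its test sentence and hypothesis 4 include it; without it the count is 19 − 3 = 16. Hypothesis 7 would add one 9-month interference test, and hypothesis 8 two WOMAC tests.

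**3. Illustration of size.** The plan has no visible figure to reproduce: sample size and event rates are not shown. Only the two-sided 0.05 level (SAP 4.0) comes from the documents. Everything else is assumed: equal arms of 20, 30, 40 or 60, a 3-month success rate of 20-40%, and identical trajectories in both arms (no treatment effect at any common time).

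Method: exact enumeration of Fisher's test. The rejection probability is the sum, over all pairs (a, b) with p < 0.05, of Bin(a; n, later rate) × Bin(b; n, 3-month rate).

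Group #2 at 20%:

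| Group #1 later rate | n=20 | n=30 | n=40 | n=60 |
|---|---|---|---|---|
| 20% (no drift) | 0.023 | 0.022 | 0.028 | 0.028 |
| 25% | 0.033 | 0.039 | 0.052 | 0.065 |
| 30% | 0.062 | 0.089 | 0.123 | 0.181 |
| 15% | 0.033 | 0.037 | 0.055 | 0.070 |
| 10% | 0.072 | 0.096 | 0.162 | 0.247 |

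Over 3-month rates of 20-40% the ranges are 2-3% with no drift, 3-7% at 5 points either way, 5-18% for a 10-point rise and 6-25% for a 10-point fall.

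**4. Direction.** Without drift, rejections split evenly between the arms. At the 20% rate, a 5-point rise puts 87-97% of rejections in favour of Group #1, and a 5-point fall puts 89-98% in favour of sham. At 10 points, 98-100% follow the drift (96-100% over 20-40%). So even where the total stays near 5%, the errors are almost all one way.

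**5. Masking.** The bias can also hide a real effect. Assume that at 12 months active is 50% and sham would have been 20%, but sham was 30% at 3 months. Power in favour of Group #1 falls from 0.60 (concurrent) to 0.26 (cross-time) at 30 per arm, and from 0.85 to 0.46 at 50 per arm.

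**6. Time-matched test.** The 3-month Fisher test under the same assumptions rejects in 2-3% of trials, whatever happens later.

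**The case against.** The strongest reply is that the plan discloses the mismatch and has already discounted it. SAP 4.0 bars claims of significance from secondary tests, the SAP gives its reason for the 3-month comparator, and the missing sham arm follows from offering crossover. Read literally, hypothesis 2 equates Group #1 at a later time with Group #2 at 3 months. Fisher's test holds its level for that null, and under drift rejection is correct.

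This lowers the severity, and no more. The exploratory label deals with strength of evidence, not with a contrast that measures something other than its name. The literal null is not the one SAP 5.2.2 states, which is no difference between the treatment groups. In 5.2.4 a significant result at a time point triggers a further test, so the results also have consequences within the plan.

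Several narrower points stand:

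- The numerical illustration is assumed throughout and covers only the Fisher endpoints, 3 + 2 = 5 of the 19 tests.
- Loss of the blinded evaluator bears directly on the survey endpoints, PGIC and interference (4 tests). Pain scores are recorded by subjects in diaries, where the issue is the subject's own knowledge. Medication change is scored by a blinded committee, so there the main problem is time.
- Some SAP sections are not visible and may already contain within-group durability analyses. That would make the fix smaller, but would not justify the cross-time tests.
- The 3-month contrast is time-matched and blinded, but its full validity still depends on the analysis set, which is a separate matter.

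**Conclusion.** The concern holds and should be fixed. The post-3-month tests in SAP 5.2.2, 5.2.3, 5.2.4, 5.2.6 and 5.2.7, with the matching parts of hypotheses 2, 3, 4, 6, 7 and 8, confound treatment with elapsed time and with the end of assured blinding. They cannot support or refute durability versus sham beyond 3 months.

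That conclusion rests on the design as written and needs no assumed number. The size and direction of the bias are unknown; the illustrative rates depend on assumed arm sizes, responder rates and drift. The primary endpoint (Weeks 5-8) and all contrasts through 3 months are unaffected by this point. With the exploratory status of the tests, that makes it a limit on what the trial can conclude about long-term effect, not a threat to its main result.

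**What to change.** - **Between-group tests.** Restrict them to Weeks 1-4, Weeks 5-8 (or the 4- and 8-week visits) and 3 months. Remove the later comparisons from hypotheses 2, 3, 4, 6, 7 and 8 in SAP 4.2 and from SAP 5.2.2, 5.2.3, 5.2.4, 5.2.6 and 5.2.7.
- **WOMAC.** Limit the test in SAP 5.2.8 to the two pairs it spells out, and align its heading and hypothesis 8.
- **Later data.** Add to the SAP: *After 3 months, Group #1 will be summarised within group with 95% confidence intervals and paired change from its own Weeks 5-8 (or 8-week) or 3-month value. These results have no concurrent control, are not protected by blinding, and are not estimates of treatment effect versus sham.*
- **Durability endpoint.** State that the durability endpoint in Protocol 4.4.2 is read as between-group through 3 months and within Group #1 thereafter.
- **9-month visit.** Reconcile its listing for medication, PGIC and interference between the headings, hypotheses and text, so that the within-group summaries cover a defined set of times.

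The cost is SAP wording and table shells. Data collection does not change and all Group #1 follow-up is still reported. What is lost is the set of exploratory 6 to 12 month p-values against sham. No reanalysis can supply a concurrent sham value after 3 months.
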